### 3.2 Primary and Secondary Endpoints and Evaluations

### 3.2.1 Primary Efficacy Endpoints and Evaluations

Non-inferiority of Eziclen®/Izinova® versus Klean-Prep® in the cleansing of the colon:

The primary efficacy will be assessed by blinded overall assessment of preparation efficacy (Cleansing Score) as determined by the colonoscopist upon completion of the examination, based on a 4-point scale:

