# 10.1.1 Populations Analysed

The primary analysis based on the primary efficacy endpoint will be performed on the mITT population. In that analysis, subjects who do not undergo colonoscopy because of inadequate preparation or preparation-related AEs will be considered as failures. In addition, robustness of primary efficacy results will be assessed by repeating the primary analysis on the PP population. The analyses of safety data will be performed based on the safety population.

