# 10.1.2 Subject Allocation and Reasons for Exclusion from the Analyses

Any major protocol deviation will be described in the Protocol Deviation Document (PDD) and its impact on inclusion in each analysis population (mITT/PP population) for any subject will be specified. The final list of protocol deviations impacting the mITT/PP population will be reviewed during the data review meeting held prior to database lock. The list will be updated to include any additional major protocol deviations impacting inclusion in the PP population.

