# **10.2** Sample Size Determination

The primary aim of the study is to show that Eziclen®/Izinova® is not inferior to Klean-Prep® in the proportion of subjects with successful colon cleansing.

A non-inferiority margin of 15% has been selected for consistency with other studies in colon cleansing preparations.

Therefore assuming a success rate (excellent or good response) of 85% in both the Eziclen®/Izinova® and Klean-Prep® groups, a one-sided alpha of 0.025 and 90% power, 120 subjects are required per treatment group. Assuming a rate dropout/non-compliance to protocol of 4% based on previous studies and taking into account that subjects will be hospitalised for treatment administration, 125 subjects will be randomised in each treatment group, i.e. 250 subjects in total. Enrolment will be completed once 250 subjects have been randomised.

The primary endpoint of treatment success will be tested sequentially (hierarchical structure) with the first test being non-inferiority test based upon the treatment difference. A rejection of the null hypothesis will trigger superiority testing based upon the treatment difference.

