#### 10.4.5 Efficacy Evaluation

As indicated in Section 7.1, the primary efficacy variable is the proportion of subjects with successful overall preparation evaluated with the scale (from 1 to 4) of the Cleansing Score as assessed by the colonoscopist.

A successful preparation will be defined as excellent (4) or good (3) preparation.

A failure preparation will be defined as:

- Fair (2) or poor (1) according to bowel cleansing
- Any subject who did not have a colonoscopy based on the investigator's assessment of the cleansing (insufficient faecal output, unclear faecal discharge, etc.) or due to preparation related AEs.
- Any subject for whom cleaning was not adequate for evaluation.
- Any subject for whom rescue treatment (saline enema) was needed.

The proportion of subjects with successful colon cleansing (graded as excellent or good) will be summarised along with the 95% confidence interval (CI) using the standard Wald asymptotic CI. The primary efficacy endpoint will be analysed using a logistics regression model including country as stratified variable, the interaction between country and treatment will be also investigated. The formal hypothesis test result (p-value) for treatment difference will be presented together with a two-sided 95% CI for the difference in success rates. The non-inferiority will be demonstrated if the lower limit of the 95% CI of that difference is higher than -15%.

If the non-inferiority is demonstrated, the superiority will be analysed based upon treatment difference. If the lower limit of the CI is greater than zero, Eziclen®/Izinova® is proven to be superior to the Klean-Prep®.

Secondary efficacy endpoints are presented in Section 7.2.

Results will be tabulated by treatment group and overall using descriptive summary statistics (mean SD, median, interquartiles and ranges) or frequency count with two-sided 95% CI when appropriate.

Time to clear effluent data will be analysed by using survival methods. The results will be presented both in summary tables (number of events, censors, median and interquartile time to event with 95% CI...) and graphically in Kaplan-Meier plots by treatment group and overall. This will be detailed in the SAP.

Other secondary endpoints will be analysed using Cochran-Mantel-Hænszel (CMH) chi-square for count (percentage) adjusting for country effect and two-way analysis of variance (ANOVA) for continuous parameters including treatment, country and their interaction as covariates.

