1.4.2 Subjects assessments

1.4.2.1 Efficacy assessments

Blinded overall assessment of preparation efficacy will be determined by the colonoscopist upon completion of the examination, based on a 4-point scale. The colonoscopist will score the quality of the bowel preparation using the following Cleansing Score (Table 1).

Score	Grade	Description
4	Excellent	No more than small bits of adherent faeces/fluid
3	Good	Small amounts of faeces or fluid not interfering with examination
2	Fair	Enough faeces or fluid to prevent a completely reliable examination
1	Poor	Large amounts of faecal residue, additional cleansing required

Table 1Cleansing Score

The primary efficacy will be assessed on the basis of preparation success or failure. The primary efficacy variable is the proportion of subjects with a successful overall preparation.

Only perfect preparations graded as excellent (4) or good (3), which allow full, reliable examination of the mucosa, will be considered as successful.

The secondary efficacy endpoints are summarised below (Table 2):

Endpoint	Timepoint	Evaluation
Colon cleansing	V2 (Colonoscopy)	Cleansing Score assessed on 4 levels (4-point scale, see Table 1).
Overall and segmental cleansing assessed by Boston Bowel Preparation Scale (BBPS)	V2 (Colonoscopy)	BBPS (see Table 3) Overall score [1]. Segmental scores (left colon (LC), transverse colon (TC), right colon (RC)).
Time to clear effluent (hours)	V1 (Treatment)	Time between first intake of prescription and first clear watery stool.
Complete procedure	V2 (Colonoscopy)	Number (%) of complete procedures defined as procedures that reached the caecum.
Time to caecal intubation (minutes)	V2 (Colonoscopy)	Time between the colonoscope introduction and the time to reach caecum.
Duration of examination (minutes)	V2 (Colonoscopy)	Time between the caecum is reached and the withdrawal of the colonoscope.
Need for rescue treatment because of inadequate preparation intake.	V2 (before colonoscopy)	Number (%) of procedures that need a rescue treatment (saline enema).
Treatment acceptability	V1 (Treatment)	Level of acceptability of treatment assessed using a 5- point Treatment Acceptability Questionnaire (see Table 4).
Need for nasogastric tube	V1 (Treatment)	Number (%) of subjects who need a nasogastric tube to complete preparation.
Treatment compliance	V1 (Treatment)	Percentage of volume of fluid taken relative to the planned volume of fluid to be taken

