2.1.1 Modified Intention-To-Treat population (mITT)

The mITT population is:

All randomised subjects who received even a partial dose of study treatment and produced a primary efficacy assessment.

Subjects will be assessed according to their randomised treatment, regardless of the treatment they receive.

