3.2.3 Missing data and outliers

3.2.3.1 Missing data

No missing value will be replaced, except for the primary analysis where the missing preparation evaluations (because of colonoscopy not done because of inadequate preparation or preparation-related AEs) will be considered as failures.

In the description of qualitative parameters, subjects with a value counted as "missing" at a visit will be identified as subjects being not assessed.

If a value required a retest, the last reliable non-missing value will be taken into account if measured before the first intake of treatment; and the first non-missing reliable value for postbaseline assessments. An assessment will be considered reliable if it is performed without any technical problem and if the result is within the range of plausible values. Any retest or unscheduled assessments performed will be included in the individual subject data listings.

If there is a significant number of missing values for a subject (or if there is confirmed data appearing spurious), a decision will be made following consultation with the sponsor regarding the handling of these data in summaries, prior to database freeze.

Any repeat or additional assessments performed will be included in the individual subject data listings.

3.2.3.2 *Missing or incomplete dates*

In all listings, missing or incomplete dates should be left as they have been recorded. However, for calculation / sorting / assignation based on dates, the following methods will be used:

- The most conservative approach will be systematically considered (i.e. if the onset date of an AE/concomitant medication is missing / incomplete, it is assumed to have occurred during the study treatment phase (i.e. a TEAE for AEs) except if the partial onset date or other data [stop date, ...] indicates differently).
- A missing/incomplete date of medical history or disease diagnosis will be assumed to have occurred before any study treatment.
- If a partial date and the associated information do not allow to state about the assignation to a group / category, all the possible groups / categories will be considered (e.g. a medication with partial start and stop dates could be considered as prior and concomitant treatment).

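### As worded, the mITT entry rule leaves out the no-colonoscopy preparation failures that the primary analysis is meant to count, and the mITT flag has no stated derivation

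*SAP*

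**What the plan says.** **Who is in the mITT.** SAP 2.1.1 (mITT) defines the set as "All randomised subjects who received even a partial dose of study treatment and produced a primary efficacy assessment". Protocol 10.1 and the synopsis (Statistical Methods) give the same definition. The requirement of an assessment is the only thing that separates mITT from ITT, which needs just randomisation and a partial dose.

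**What the assessment is.** Protocol 3.2.1 describes the Cleansing Score "as determined by the colonoscopist upon completion of the examination". SAP 1.4.2.1 agrees: "Blinded overall assessment of preparation efficacy will be determined by the colonoscopist upon completion of the examination".

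**How subjects with no colonoscopy are handled.** Protocol 10.1.1 names the mITT as the primary analysis set and continues: "In that analysis, subjects who do not undergo colonoscopy because of inadequate preparation or preparation-related AEs will be considered as failures". SAP 2.5 repeats this. The failure list in Protocol 10.4.5 includes "Any subject who did not have a colonoscopy based on the investigator's assessment of the cleansing", and extends it to preparation-related AEs. SAP 3.2.1.1 and SAP Appendix 1 item 3 carry the same list. SAP 3.2.3.1 makes one exception to its rule of no imputation: "the missing preparation evaluations (because of colonoscopy not done because of inadequate preparation or preparation-related AEs) will be considered as failures".

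**How the set is selected.** The primary code in SAP 3.2.1.1 keeps records with MITTFL='Y'. The list of derived data in SAP Appendix 1 does not say how MITTFL is set.

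**The concern.** A subject who took the preparation but was never scoped, because the bowel was not clean or the preparation caused an AE, is a plain treatment failure. The documents say so several times. But that subject has no score given at the end of an examination, and SAP 3.2.3.1 itself calls the evaluation missing. Applied literally, the entry rule removes the subject before the failure rule can act.

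The mITT carries the non-inferiority test and the superiority test that follows it. Removing true failures from one arm's denominator raises that arm's success rate. If such subjects were mainly in the Eziclen/Izinova arm, non-inferiority would be easier to show than it should be.

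No planned robustness run on the primary difference would reveal this. The PP set requires a colonoscopy (SAP 2.1.2), so it omits the same subjects. The identity-link and bootstrap runs use the same mITT filter.

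**Working it through.** **Inputs from the documents** (Protocol 10.2 and 10.3; SAP 1.4.4 and 3.1.5): 85% success in both arms, margin 15 points, one-sided alpha 0.025, power 90%, 120 per arm, 125 per arm after a 4% allowance. Non-inferiority is shown if the lower limit of the two-sided 95% CI for the difference (test minus comparator) is above -15%.

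**The plan's own figure.** n = (1.960 + 1.282)² × 2 × 0.85 × 0.15 / 0.15² = 119.1, so 120 per arm; 120 / 0.96 = 125. The sample size reproduces and is not affected by this point.

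**Assumptions.** The documents give no rate of no-colonoscopy preparation failures. I take 125 treated per arm, a crude Wald interval (the planned analysis adjusts for country), and k such subjects in an arm, all true failures, dropped under the literal rule.

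**One worked case, k = 3 in the test arm and 0 in the comparator.** Lower limit = d - 1.96 × √[p₁(1-p₁)/n₁ + p₂(1-p₂)/n₂].

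- Counted as failures: 97/125 v 106/125. d = 77.60 - 84.80 = -7.20 points, SE 4.92, lower limit -16.85. Non-inferiority is not shown.
- Dropped: 97/122 v 106/125. d = 79.51 - 84.80 = -5.29 points, SE 4.86, lower limit -14.83. Non-inferiority is shown.

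With the comparator at 106/125, only test-arm totals of 97, 98 and 99 successes change the conclusion:

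| Test successes | Lower limit, counted (n = 125) | Lower limit, dropped (n = 122) |
|---|---|---|
| 96 | -17.71 | -15.72 |
| 97 | -16.85 | -14.83 |
| 98 | -15.97 | -13.93 |
| 99 | -15.10 | -13.02 |
| 100 | -14.22 | -12.11 |

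**Error at the margin.** Set the true rates over all treated subjects at 70% (test) and 85% (comparator). If k true failures are dropped from an arm, the successes among the scored follow Bin(125 - k, p × 125/(125 - k)). For k = 3 in the test arm the rate among the scored is 0.70 × 125/122 = 0.717. Summing the exact joint probability of all outcomes with a Wald lower limit above -15% gives:

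| Dropped, test v comparator | One-sided error |
|---|---|
| 0 v 0 | 2.64% |
| 1 v 0 | 3.31% |
| 3 v 0 | 5.36% |
| 3 v 3 | 2.20% |
| 5 v 5 | 2.03% |
| 0 v 3 | 0.95% |

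**At the planned rates** (85% v 85%), the two rules give different conclusions in 4.97% of trials when 3 v 0 are dropped.

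**The case against.** The strongest reply is that the wording can be read consistently. Protocol 7.3.1, which is headed as the primary efficacy assessment, says that efficacy is judged on preparation success or failure, and the failure list covers subjects with no colonoscopy. On that reading an assigned failure is the assessment, and these subjects are in the mITT. The synopsis puts the population and the failure rule in consecutive sentences, and the exception in SAP 3.2.3.1 has an effect only if these subjects are in the set. The primary code also selects the derived success parameter, not the raw score. All of this stands as evidence of intent. It does not settle membership: no passage says that an assigned failure meets the entry rule, the same section 7.3.1 goes on to describe the colonoscopist's score, and SAP 3.2.3.1 calls the evaluations missing.

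Protocol 10.1.2 says that for major deviations "its impact on inclusion in each analysis population (mITT/PP population) for any subject will be specified". That deviation document may resolve the question, but it is not part of the plan reviewed here.

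Three stronger readings are tempting and should be resisted.

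- A reader might infer that the trial will exclude these subjects. The filter MITTFL='Y' does not show that, because no derivation of the flag is given.
- A reader might take one arm's full allowance, 4% of 125 = 5 subjects, as the likely loss. The protocol says "Assuming a rate dropout/non-compliance to protocol of 4% based on previous studies", which covers every kind of dropout and non-compliance, not only unscoped preparation failures. The nasogastric tube and rescue enema may also keep such cases few, and a subject who is rescued and then scored stays in the mITT as a failure.
- A reader might extend the point to treated subjects unscored for other reasons. PP requires a colonoscopy, not a score, so such subjects are not all outside it, and dropping losses unrelated to preparation leaves the error at about 2.6%.

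**Conclusion.** The inconsistency is real and appears in both documents. It is a defect of wording and flag definition, not proof that failures will be removed: the intent to count them is explicit. Harm needs three things together: a flag programmed from the literal definition, losses falling mainly in the test arm, and a result near the margin. Under the stated assumptions (125 treated per arm, crude Wald interval, all dropped subjects true preparation failures in the test arm only), the one-sided error rises from 2.6% to 3.3% with one such subject and to 5.4% with three. Balanced losses do not inflate it, and losses in the comparator only make it smaller. Because the ambiguity sits in the set that carries both hierarchical tests, and the PP analysis cannot expose it, it should be resolved in the text and not left to the programmer.

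**What to change.** In the protocol (synopsis and 10.1) and in SAP 2.1.1 (mITT), define the mITT as all randomised subjects who received any study drug and who either have a Cleansing Score or meet one of the failure criteria in Protocol 10.4.5 and SAP 3.2.1.1. Add a matching MITTFL derivation to SAP Appendix 1, so that subjects with no colonoscopy because of inadequate preparation or preparation-related AEs are flagged into the set and scored as failures. Do this before the randomisation lists are released for the final analysis, so that the choice cannot follow the result.

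The cost is one sentence in each definition and one derivation rule. The sample size, endpoint and model stay as they are. Reported success rates may be slightly lower than under the literal flag.

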2.1.2 Per Protocol population (PP)

The PP population is:

All subjects in the ITT population, who have undergone the colonoscopy procedure and for whom no major protocol violation/deviation impacting analyses (as defined in the Protocol Deviation Document) occurred.

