#### 10 STATISTICS

# **10.1** Analyses Populations

The following population will be used during statistical analyses:

- Screened population: All subjects screened (i.e. who signed the informed consent).
- Safety population: All randomised subjects with at least a partial dose of study medication. Subjects will be assessed according to the treatment received.
- **Intention to treat (ITT) population**: All randomised subjects who received even a partial dose of study drug. Subjects will be assessed according to their randomised treatment, regardless of the treatment they receive.
- Modified Intention to treat Analysis Set (mITT): All randomised subjects who received even a partial dose of study treatment and produced a primary efficacy assessment.
- **Per protocol (PP) population**: All subjects in the ITT population, who have undergone the colonoscopy procedure and for whom no major protocol violations/deviations occurred.

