2.4 Other populations

2.4.1 Screened population

The screened population is:

All subjects screened (i.e. who signed the informed consent).

23/62

F-FR-58800-003

2.5 **Primary populations**

The primary analysis based on the primary efficacy endpoint will be performed on the mITT population. In that analysis, subjects who do not undergo colonoscopy because of inadequate preparation or preparation-related AEs will be considered as failures. In addition, robustness of primary efficacy results will be assessed by repeating the primary analysis on the PP population.

The analyses of safety data will be performed based on the safety population.

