3.2.1.1 Primary efficacy analyses

The primary endpoint of treatment success will be tested sequentially (hierarchical structure) with the first test being non-inferiority test based upon the treatment difference. A rejection of the null hypothesis will trigger superiority testing.

The two hypothesis tests are hierarchically structured so that the second test (superiority) will only be considered if the first test (non-inferiority) is accepted. The superiority test is powered

to detect an absolute difference of 18 %. There is no alpha adjustment for the second test as a result of the hierarchical testing.

The primary efficacy analysis will be based on the mITT population and repeated on the PP population in order to assess the robustness of the results.

The primary efficacy variable is the proportion of subjects with successful overall preparation evaluated with the scale (from 1 to 4) of the Cleansing Score as assessed by the colonoscopist.

A successful preparation will be defined as excellent (4) or good (3) preparation.

A failure preparation will be defined as:

- Fair (2) or poor (1) according to colon cleansing score,
- Any subject who did not have a colonoscopy based on the investigator's assessment of the cleansing (insufficient faecal output, unclear faecal discharge, etc.) or due to preparation related AEs,
- Any subject for whom cleaning was not adequate for evaluation,
- Any subject for whom rescue treatment (saline enema) was needed.

The proportion of subjects with successful colon cleansing (graded as excellent or good) will be summarised along with the 95 % CI using the standard Wald asymptotic CI using the following SAS code:

```
proc freq data=ADCC(where=(PARAM='Successful overall preparation' and MITTFL='Y'));
```

```
table AVALC / missing binomial(level='Yes' cl=wald);
```

by TRTP;

run;

The primary efficacy endpoint will be analysed using a logistic regression model including treatment and country as covariates as well as the interaction between treatment and country if it is significant (i.e. p < 0.10, as interaction tests have low power) using the following SAS code providing the adjusted proportions with their 95 % CI thank to ilink option, and with the option firth in the model with interaction since there might otherwise be a quasi-complete separation of data points affecting the validity of the model:

proc logistic data=ADCC(where=(PARAM='Successful overall preparation' and MITTFL='Y'));

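### The per-protocol set drops subjects whose colonoscopy was cancelled for preparation reasons, whom the plan counts as failures, so it cannot check robustness to that failure

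*SAP*

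**What the plan says.** SAP 2.1.2 limits the PP set to "All subjects in the ITT population, who have undergone the colonoscopy procedure and for whom no major protocol violation/deviation impacting analyses" occurred. Protocol 10.1 has the same colonoscopy condition: "All subjects in the ITT population, who have undergone the colonoscopy procedure and for whom no major protocol violations/deviations occurred". In both, having had the colonoscopy is one condition and being free of excluding deviations is another.

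The endpoint rules treat a colonoscopy cancelled for preparation reasons as a failure. For the primary mITT analysis, SAP 2.5 states that "subjects who do not undergo colonoscopy because of inadequate preparation or preparation-related AEs will be considered as failures", and Protocol 10.1.1 agrees. The list of failures in SAP 3.2.1.1 includes "Any subject who did not have a colonoscopy based on the investigator's assessment of the cleansing" or because of preparation-related adverse events. Protocol 10.4.5 and SAP Appendix 1 carry the same item. SAP 3.2.3.1 makes it the single exception to the rule that missing values are not replaced.

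SAP 2.5 and Protocol 10.1.1 then assign PP its role: the primary analysis is to be repeated on it to assess robustness.

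**The concern.** A subject who takes the whole preparation, breaks no rule and is then not scoped because the bowel is not clean is a treatment failure. The primary analysis counts that subject as one. The PP set removes the subject from numerator and denominator alike. The removal follows from a post-randomisation outcome that is part of the endpoint, and no protocol violation is needed. No text puts these subjects back: the failure rule in SAP 2.5 is written for the mITT analysis, and within PP it would have nobody to act on.

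PP is the only planned repeat of the primary non-inferiority analysis in a second population. The identity-link model and the bootstrap in SAP 3.2.1.1 both stay in mITT. If the two preparations differ in how often they lead to cancellation, PP discards part of the difference that the trial is meant to measure. It may then agree or disagree with mITT for a reason unrelated to adherence.

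**Working it through.** **Inputs.** Protocol 10.2 gives "a one-sided alpha of 0.025 and 90% power, 120 subjects are required per treatment group", a margin of 15 points ("A non-inferiority margin of 15% has been selected for consistency with other studies in colon cleansing preparations"), success rates from "assuming a success rate (excellent or good response) of 85% in both the" two groups, and attrition ("Assuming a rate dropout/non-compliance to protocol of 4% based on previous studies"). The documents give no expected cancellation rate for either arm, so every rate below is an assumption.

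**The plan's own figure.** n per arm = 2 × 0.85 × 0.15 × (1.960 + 1.282)² / 0.15² = 119.1, rounded up to 120. With 4% attrition, 120 / 0.96 = 125. Both stated figures reproduce.

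**Single-trial example.** Differences are Eziclen minus Klean-Prep, with unadjusted Wald 95% intervals: d ± 1.96 × √[p₁(1−p₁)/n₁ + p₂(1−p₂)/n₂]. The SAP's country adjustment is left out, and no other PP exclusions are assumed. Take 95 successes of 120 on Eziclen and 102 of 120 on Klean-Prep, with cancelled subjects among the failures.

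| Cancelled, Eziclen / Klean-Prep | Analysed | Difference (points) | 95% CI | Lower limit above −15? |
|---|---|---|---|---|
| counted as failures (mITT) | 95/120 vs 102/120 | −5.8 | −15.5 to 3.8 | no |
| 5 / 2, removed (PP) | 95/115 vs 102/118 | −3.8 | −13.1 to 5.5 | yes |
| 5 / 5, removed (PP) | 95/115 vs 102/115 | −6.1 | −15.1 to 2.9 | no |
| 2 / 5, removed (PP) | 95/118 vs 102/115 | −8.2 | −17.4 to 1.0 | no |

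The same mITT data can give a PP result on either side of the margin, depending on how the cancellations split.

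**Repeated trials at the margin.** Let true success, counting cancellations as failures, be 70% on Eziclen and 85% on Klean-Prep, with 120 per arm. If fractions c₁ and c₂ are cancelled, the PP success rates are 0.70/(1−c₁) and 0.85/(1−c₂). The last column is the simulated share of trials in which the PP lower limit exceeds −15 points. The mITT share is about 2.6% in every row.

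| c₁ / c₂ | PP rates | PP true difference (points) | PP passes |
|---|---|---|---|
| 0% / 0% | 70.0% vs 85.0% | −15.0 | 2.6% |
| 2% / 0% | 71.4% vs 85.0% | −13.6 | about 4.7% |
| 5% / 2% | 73.7% vs 86.7% | −13.1 | about 6.0% |
| 5% / 5% | 73.7% vs 89.5% | −15.8 | about 1.9% |
| 0% / 5% | 70.0% vs 89.5% | −19.5 | about 0.2% to 0.3% |

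**Where the direction changes.** Setting 0.70/(1−c₁) − 0.85/(1−c₂) = −0.15 gives c₁ ≈ 1.2 c₂. At the margin, PP moves toward non-inferiority only when Eziclen's cancellation rate exceeds about 1.2 times Klean-Prep's.

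**Truly equal arms (85% each).** By normal approximation PP passes in 90.2% of trials with no cancellations, 92.4% with 2% in each arm, and 82.3% with 2% on Eziclen and 5% on Klean-Prep.

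**The case against.** The strongest reply is that PP decides nothing. The primary analysis is on mITT, no rule requires success on PP, and a trial that fails on mITT has failed whatever PP shows. This stands: the percentages above describe the PP check and are not the trial's type I error.

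A reader might also infer that the definition pushes PP toward non-inferiority as a rule. The documents do not support that. They give no cancellation rates, and nothing in them places cancellations mainly on Eziclen. Protocol 1.1 describes large-volume polyethylene glycol solutions as often poorly tolerated, which if anything points to the comparator. Equal cancellation at the margin makes PP slightly stricter, and an excess on Klean-Prep makes it much stricter.

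Two further points limit the size. Cancellations may be few: subjects are in hospital, and the protocol provides for a nasogastric tube and for saline enema. Subjects who needed an enema or scored fair or poor, but were scoped, remain in PP as failures unless a deviation removes them. Nor would an imbalance be hidden. SAP 3.2.4 tabulates reasons for exclusion from each population by treatment group and adds a flow chart of colonoscopies performed, and SAP 3.2.5 counts them by arm.

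None of this restores the excluded failures. The tables would show that PP had lost them, but PP would still not be a repeat of the primary analysis.

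**Conclusion.** The point holds as a defect of the supportive analysis. The PP set excludes, by outcome, a category that the plan itself counts as failure, so it cannot test robustness to that category. It is biased by any imbalance in cancellations: toward non-inferiority if Eziclen clearly has more, and against it if Klean-Prep has more or, slightly, if the rates are equal at the margin. In the scenarios tabulated, the PP pass rate at the margin runs from about 0.3% to 6.0%, against 2.6% with no cancellations. This rests on assumed cancellation rates, 120 subjects per arm, no other PP exclusions and unadjusted Wald limits. The exclusion itself follows from the text and needs no assumption. What is at stake is the credibility of the robustness check. The change should be made, but the primary conclusion does not depend on it.

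**What to change.** In SAP 2.1.2, define PP as ITT subjects who either had the colonoscopy, or did not have it because of inadequate preparation or preparation-related adverse events (counted as failures), and who have no major deviation impacting analyses. Record the change in SAP section 5, where version 4.0 already records a revision of the PP definition. Align Protocol 10.1 if the protocol is amended for other reasons; an amendment for this alone would generally need ethics committee approval under Protocol 12.1.1. Make the change before database lock.

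The mITT definition asks for a primary efficacy assessment to have been produced, so it is worth stating there too that these subjects belong to mITT.

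The cost is a small document change and a slightly lower PP success rate. No new data are needed, because the failure rule already requires the reason why a colonoscopy was not done.
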